**Cryoprecipitate** is made from FFP and contains various proteins including fibrinogen. It contains higher concentrations of fibrinogen than FFP and some (but not all) coagulation factors, so less volume is needed. The minimum amount of fibrinogen required by standards of the American Association of Blood Banks is 150 mg per bag of cryoprecipitate; current preparations yield a median of 388 mg per bag, but the amount of fibrinogen is variable and cannot be determined accurately. A single unit of cryoprecipitate also contains variable amounts of FVIII, FXIII, von Willebrand factor (vWF), fibronectin and platelet microparticles (Callum et al., 2009). Therefore, the use of cryoprecipitate for fibrinogen replacement alone exposes the patient to potentially unneeded coagulation proteins which could increase the risk of thrombosis (Elliott and Aledort, 2013; Franchini and Lippi, 2012). Cryoprecipitate was withdrawn from most European countries some years ago because of safety concerns (Karkouti et al., 2018; Schochl et al., 2013) but remains available in Scandinavia, the UK and the USA, essentially for the purpose of fibrinogen replacement.

In summary fibrinogen concentrate seems to have certain advantages over other replacement therapies like FFP and cryoprecipitate, such as precisely determined high amounts of purified fibrinogen dissolved in a small volume, low risk of pathogen transmission and instant administration without need for thawing or testing AB0 blood group compatibility (Warmuth et al., 2012).

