As there is no guideline on the clinical investigation of fibrinogen in patients with uncontrolled severe hemorrhage in acquired hypofibrinogenaemia available, the EMA guideline on core SmPC for human fibrinogen products (EMA (Committee for Medicinal Products for Human Use), 2015) has been taken into account when planning this phase III study in acquired fibrinogen deficiency. Furthermore, currently ongoing clinical studies with fibrinogen concentrate as well as recently finalized clinical studies in this clinical setting (Roy et al., 2020) have been considered.

BT524 will be developed as complementary therapy to management of uncontrolled severe hemorrhage in acquired hypofibrinogenaemia caused by major surgeries associated with major blood loss. As it is expected that BT524 will show a safety advantage over the standard treatment with FFP/cryoprecipitate, an efficacy comparison to the standard is required to allow a risk-benefit assessment to be made for BT524.

Therefore, the present prospective, multi-center, randomized, active-controlled, pivotal phase III non-inferiority study aims to investigate efficacy and safety of BT524 in subjects with acquired hypofibrinogenaemia.

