#### Special precautions for BT524 administration

All plasma-derived human products may lead to allergic or anaphylactic reactions. Thus, the administration of BT524 will be performed under medical supervision where proper medical care for allergic or anaphylactic reactions can be provided. If allergic or anaphylactic-type reactions occur, the infusion must be stopped immediately. In case of anaphylactic shock, standard medical treatment for shock must be applied.

Prothrombin time PT(INR), activated partial thromboplastin time (aPTT), prothrombin fragments  $F_{1+2}$ , thrombin-antithrombin III complex (TAT), D-dimer, PS, PC, antithrombin III (AT III) activity, thrombin time (TT), thrombin generation test (TGT) and further coagulation parameters are monitored regularly to detect a hypercoagulable state.

Changes in vital signs (including pulse [heart rate], blood pressure, respiratory rate, body temperature) are monitored during the surgery and according to the flow chart (see section III).

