## 10.7 Safety Analysis

AEs will be coded using the most current version of Medical Dictionary for Regulatory Activities (MedDRA®). The version used will be defined in the SAP. Incidence rates (i.e., number and percentage of affected subjects) will be calculated for the coding levels *SOC* and *preferred term* and will be presented by treatment arm. Further analyses of AEs will focus on seriousness, intensity, causal relationship to IMP, and outcome. IRAE including SAEs etc. will be displayed in detail.

Safety laboratory assessments (hematology, clinical chemistry, urinalysis and coagulation parameters) will be categorized with respect to the laboratory specific reference ranges as normal/abnormal. Abnormal values will be further classified with respect to clinical relevance. Changes over time will be described by means of "shift-tables" by treatment arm as well as summarized with descriptive statistics by time point and treatment arm.

Vital signs data will be summarized descriptively before and after surgery by treatment arm.

The frequency of thrombosis and of TEEs, virus status, exposure data and concomitant medication will be summarized by treatment arm.

All safety analyses will be based on the SAF.

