12.6.3 Laboratory Data

The following clinical laboratory variables will be summarized for the overall population, and separately by type of surgery (spinal and abdominal surgery):

Hematology	Red blood cells (RBC), white blood cells (WBC), platelet count, hemoglobin, hematocrit, neutrophils (absolute and %), lymphocytes (absolute and %), eosinophils (absolute and %) and basophils (absolute and %)
Biochemistry	Aspartate aminotransferase, alanine aminotransferase, creatinine, creatinine clearance (Cockcroft and Gault), blood urea nitrogen (BUN), urea, gamma-glutamyltransferase (γ -GT), alkaline phosphatase (AP), total bilirubin, direct bilirubin, indirect bilirubin, potassium, sodium, calcium and chloride
Urinalysis	pH, blood, WBC, protein, glucose, ketone bodies, nitrite, bilirubin and urobilinogen
Markers of Coagulation	PT, INR, aPTT, TAT, F1+2, D-dimer, PS, PC, AT III, TT and ETP(TGT)
Coagulation factors	FII, FV, FVII, FVIII, FIX, FX, FXI, FXIII and vWF

Note: Protein C (PC) is also referred to as Factor XIV. Direct bilirubin and indirect bilirubin are only assessed in case of an elevated bilirubin value and are thus not generally included in statistical summaries.

Quantitative laboratory parameters reported as "< x" or "y" > will be imputed with x/2 and y, respectively, for inclusion in summary statistics. The reported value will be presented in listings.

Descriptive statistics for clinical laboratory values (in SI units) and changes from baseline at each scheduled assessment visit (as stated in Flowchart of study) with the exception of urinalysis parameters and direct/indirect bilirubin will be presented by treatment and treatment arm.

Laboratory results of all hematology, biochemistry, urinalysis parameters and PT/INR, aPTT will be categorized with respect to the laboratory specific reference ranges as normal/abnormal (i.e., high [H], low [L], where applicable). Abnormal values will be further classified with respect to clinical relevance by the investigator. The results and percentages will be summarized by visit and overall for each treatment and treatment arm.

Shifts from baseline to each post-baseline visit for all laboratory variables (except direct and indirect bilirubin) will be summarized by treatment and treatment arm using number and percentage of subjects.

In addition, a shift summary of hematology for number of subjects with change from normal or not clinical significant to clinical significant will be presented.

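### SAP 12.6.3 limits the normal/abnormal and clinical-relevance classification of coagulation results to PT/INR and aPTT, an undeclared narrowing of protocol 10.7 that leaves out 17 of the 20 listed variables

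*SAP*

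**What the plan says.** Protocol 10.7 sets the plan: "Safety laboratory assessments (hematology, clinical chemistry, urinalysis and coagulation parameters) will be categorized with respect to the laboratory specific reference ranges as normal/abnormal". It adds: "Abnormal values will be further classified with respect to clinical relevance". Shift tables by treatment arm follow directly. Nothing in the section separates one coagulation test from another.

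SAP 12.6.3 lists 11 markers of coagulation (PT, INR, aPTT, TAT, F1+2, D-dimer, PS, PC, AT III, TT, ETP by TGT) and nine coagulation factors: "FII, FV, FVII, FVIII, FIX, FX, FXI, FXIII and vWF". Its classification sentence reads: "Laboratory results of all hematology, biochemistry, urinalysis parameters and PT/INR, aPTT will be categorized with respect to the laboratory specific reference ranges as normal/abnormal". Out-of-range results in that scope are then rated for clinical relevance and tabulated by visit and overall. The next paragraph is wider: "Shifts from baseline to each post-baseline visit for all laboratory variables (except direct and indirect bilirubin) will be summarized", as counts and percentages of subjects.

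SAP 4.1 declares changes to the FAS and mFAS, the steps for non-normal data, the addition of overall mortality, and imputation. It declares none for laboratory analysis.

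Protocol 9.2.1.4 has the investigator rate every laboratory result at one of three levels: in range, out of range but not relevant, or out of range and relevant. The rating is made in the eCRF or in the central laboratory's web tool.

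**The concern.** A planned safety tabulation shrinks between protocol and SAP without being declared. The variables that drop out are those closest to the main safety question. Protocol 6.11 (special precautions for BT524) names ten tests and says that these and "further coagulation parameters are monitored regularly to detect a hypercoagulable state". The protocol's Introduction states that "it is expected that BT524 will show a safety advantage over the standard treatment with FFP/cryoprecipitate", and argues that using cryoprecipitate for fibrinogen replacement alone "exposes the patient to potentially unneeded coagulation proteins which could increase the risk of thrombosis". FVIII, FXIII and vWF, which it names among the contents of cryoprecipitate, are among the unclassified variables. Counts by arm of abnormal and of clinically relevant results on these tests bear on that argument.

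The SAP is also inconsistent within one section. A shift table in counts and percentages needs categories, and the only categories 12.6.3 defines sit in the sentence that leaves these variables out.

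**Working it through.** The documents state no figure on this point, so the check is a count and a comparison of texts.

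1. **Variables listed (SAP 12.6.3).** Markers 11 + factors 9 = 20. Fibrinogen itself (FIBTEM A10, MCF, Clauss) is analysed under efficacy in SAP 12.5.3.1 and is not in this list.
2. **Variables classified.** PT, INR and aPTT = 3.
3. **Variables left out.** 20 − 3 = 17, and 17/20 = 85%. With PT/INR counted as one variable the list has 19 and the classified set 2; 19 − 2 is still 17.
4. **Spine subjects only.** TGT and vWF apply to PMP surgery only (SAP 7.2.3), so 20 − 2 = 18 are listed and 18 − 3 = 15 are left out (15/18 = 83%).
5. **Hypercoagulability panel (protocol 6.11).** PT(INR), aPTT, F1+2, TAT, D-dimer, PS, PC, AT III, TT, TGT = 10. Two are classified, so 8 are left out.
6. **Could 'coagulation parameters' in protocol 10.7 mean only PT and aPTT?** No. Protocol 6.11 uses the term for tests beyond the ten it names, and protocol 9.2.3 makes changes in both markers and factors safety endpoints.
7. **Could the protocol version explain it?** The SAP cites protocol 4.0 and 4.2 UK; the version at hand is 4.3 UK. The amendment log for 4.3 shows only an editorial change to 10.1 within section 10, and nothing for 10.7.

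Output for the 17 variables, planned against remaining:

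| Output | Protocol 10.7 | SAP 12.6.3 |
|---|---|---|
| Descriptive statistics by time point | yes | yes |
| Shift tables | yes | yes, categories not defined |
| Normal/abnormal classification table | yes | no |
| Clinical relevance of abnormal values | yes | no |

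**What the shift tables would recover.** If they use normal/high/low, the totals at each visit give the number of subjects in and out of range by arm, among those with a baseline and a visit value. They would not show clinical relevance. If they used the three-level rating in protocol 9.2.1.4, relevance would appear but direction (high or low) would not. The SAP does not say which applies.

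**What the AE tables would recover.** Under protocol 9.2.1.4 a clinically relevant out-of-range value is an AE, but one that is a sign of an AE already reported is recorded as a symptom of it, not separately. AE tables therefore cannot give the number of clinically relevant results per test.

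**The case against.** The strongest case against is that little is lost. SAP 4.0 says the SAP is to be read together with the protocol. Protocol 10.7 introduces shift tables immediately after the normal/abnormal classification, and protocol 9.2.1.4 rates every result, so the categories are available. Summary statistics and changes from baseline remain for all 20 variables, as do listings. Thrombosis and TEE have their own AESI tables. The DSMB receives the coagulation markers and factors unblinded (protocol 9.4). The restriction may also have a practical reason. As far as protocol Table 1 can be read, PT/INR and aPTT are local tests while most other markers and the factors are central, and ratings of central results may sit in a different system. The separate TFL specifications may define the shift categories. Protocol 9.2.1.4 itself notes standardisation problems with thrombin generation assays.

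Most of this stands, and it sets the size of the point. A reader might infer that the shift tables for the 17 variables cannot be produced, or that abnormal coagulation results would go unrecorded. The documents support neither: the protocol supplies categories and requires the ratings, so per-visit counts in and out of range would largely survive in the shift tables. Nor does multiplying tests by visits give a measure of harm. That counts scheduled results, and the number that would be abnormal cannot be derived from the documents.

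Three things are not answered. The clinical-relevance tabulation and the separate classification table are dropped for 17 variables. SAP 4.1 does not declare it. The local/central reason is a guess, since the SAP gives none. DSMB review during the trial does not replace a planned table in the study report.

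**Conclusion.** The point holds as an undeclared narrowing of a planned descriptive safety analysis, together with shift tables for which the SAP sets no categories. It affects 17 of 20 listed coagulation variables and 8 of the 10 tests in protocol 6.11. What is lost is tabulation, not data capture. The primary test, alpha and sample size are untouched, so this is a low-priority improvement.

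The conclusion assumes that the classification sentence in SAP 12.6.3 is meant literally, that the ratings required by protocol 9.2.1.4 are collected for central results, and that the TFL specifications (not available here) do not already restore the wider scope. If they do, they conflict with the SAP sentence and the wording still needs correcting.

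**What to change.** In the classification sentence of SAP 12.6.3, replace 'PT/INR, aPTT' by 'all markers of coagulation and coagulation factors listed above', so that normal/high/low and clinical relevance are tabulated by visit and overall. Name as an exception any test without a laboratory reference range, possibly ETP by TGT. State in the shift paragraph that it uses the same normal/high/low categories.

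If the narrowing is deliberate, declare it with its reason in SAP 4.1 and limit the shift paragraph to the classified variables.

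The cost is table programming and possibly a transfer of ratings from the central laboratory's tool. The downside is more output: many values may be abnormal around major surgery in both arms, so the tables should be read by arm and visit.

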12.6.4 Vital Signs

Descriptive statistics for vital signs (systolic and diastolic blood pressure, pulse rate, respiratory rate and body temperature) and their changes from baseline at each scheduled study visit will be presented by treatment and treatment arm. This will be repeated by surgery type.

The overall vital signs monitoring results during surgery will be tabulated by number and percentage of subjects in each treatment, treatment arm and overall. This will be repeated by surgery type.

All vital signs will be listed for the SAF.

12.6.5 Physical Examinations

All the physical examination parameters will be listed for the SAF.

12.6.6 Viral Status

A shift table from screening to closing visit for virus serology parameters (hepatitis B, hepatitis C and HIV) will be summarized by treatment and treatment arm using number and percentage of subjects.

Listings for viral status will be created respectively for the SAF.

13.0 Validation

PPD goal is to ensure that each TFL delivery is submitted to the highest level of quality. Our quality control procedures will be documented separately in the study specific programming quality control plans.

14.0 References

Appendix 1 Tables, Figures, Listings, and Supportive SAS Output Appendices

Clinical Study Report:

Please see the separate document: Biotest 995 TFL Specifications.

DSMB:

Please see the separate documents for the DSMB Charter and a List of DSMB TFL Specifications.

Blinded Sample Size Recalculation:

Please see the separate document: Biotest 995 TFL Specifications for Sample Size Recalculation.

Interim Analyses for Sample Size Assessment:

Please see the separate document: Biotest 995 TFL Specifications for Interim Analysis of Sample Size.
